6. STUDY POPULATION ANALYSES

6.1. Overview of Planned Study Population Analyses

The study population analyses will be based on the Safety analysis set.

Study population analyses including analyses of subject disposition, demographic and baseline characteristics, medical history, prior and concomitant medications. Additionally, including tobacco usage and alcoholic abuse.

A two sample binomial test will be applied for primary endpoints to calculate p-value comparing binomial proportions for incidence of COVID-19 symptoms and Hospitalizations due to COVID-19 symptoms.

p-value for treatment difference using one-way Analysis of variance (ANOVA) is displayed for baseline characteristics. A standard analysis of covariance (ANCOVA) model will be applied for secondary endpoints followed by Tukey's multiple comparison test to test the the significance of the effects of the treatment. The model includes treatment as fixed factor.

Details of the planned displays are presented in Appendix 5: List of Data Displays.

Categorical variables will be summarized by the number and percentage of subjects, and the continuous parameters will be summarized by n, mean, standard error of mean, median, sample standard deviation, minimum and maximum unless otherwise specified.

Disposition summary includes, subject screened, randomized and disposition at end of study – Week 26 along with reasons for withdrawals will be presented based on number of subjects and percentage. Subjects in different analysis populations also will be presented.

Protocol Number: HBCOVID02
Hope Biosciences
Statistical Analysis Plan

Confidential

Date: 14-Oct-2021
Version: 1.0
Status: Final

7. EFFICACY ANALYSES

7.1. Primary Efficacy Analyses

7.1.1. Endpoint / Variables

The primary endpoints are incidence of COVID-19 symptoms and Hospitalizations due to COVID-19 symptoms after Week 26 end of study.

7.1.2. Summary Measure

Binomial proportions difference between treatments.

7.1.3. Population of Interest

The primary efficacy analyses will be based on the efficacy analysis set population, unless otherwise specified.

7.1.4. Statistical Analyses / Methods

Details of the planned displays are provided in Appendix 5: List of Data Displays.

7.1.4.1. Statistical Methodology Specification

Incidence of Hospitalizations due to COVID-19 symptoms:

The primary endpoint analysis is the comparison between HB-adMSCs treatments vs Placebo are described in this table.

Primary endpoint will be analysed using the two sample Binomial proportion model for the comparison of HB-adMSCs 200MM vs. Placebo, HB-adMSCs 100MM vs. Placebo and HB-adMSCs 50MM vs. Placebo to test the the significance of the effects of the treatment.

Incidence of COVID-19 symptoms:

The primary endpoint analysis is the comparison between HB-adMSCs treatments vs Placebo are described in this table.

Primary endpoint will be analysed using the two sample Binomial proportion model for the comparison of HB-adMSCs 200MM vs. Placebo, HB-adMSCs 100MM vs. Placebo and HB-adMSCs 50MM vs. Placebo to test the the significance of the effects of the treatment.

Protocol Number: HBCOVID02
Hope Biosciences
Statistical Analysis Plan

Confidential

Date: 14-Oct-2021
Version: 1.0
Status: Final

7.2. Secondary Efficacy Analyses

7.2.1. Endpoints / Variables

Change from baseline to the end of study period, Week 26 in,

- Leukocyte differential counts
- C-Reactive Protein
- TNF-alpha
- IL-6
- L-10
- SF-36 questionnaire score

7.2.2. Summary Measures

Least square mean (LSM) and LSM mean difference between treatments.

7.2.3. Population of Interest

The secondary efficacy analyses will be based on the Efficacy analysis set population, unless otherwise specified.

7.2.4. Statistical Analyses / Methods

Details of the planned displays are provided in Appendix 5: List of Data Displays.

7.2.4.1. Statistical Methodology Specification

Change from baseline to Week 26 of treatment:

The secondary endpoint analysis is the overall treatment comparison between HB-adMSCs treatments and placebo. A pair-wise comparison of HB-adMSCs 200MM vs Placebo, HB-adMSCs 100MM vs Placebo and HB-adMSCs 50MM vs Placebo are also described in this table.

Secondary endpoint will be analysed using the standard ANCOVA model followed by Tukey's multiple comparison test to test the the significance of the effects of the treatment. The model includes treatment as fixed factor and the baseline value as a covariate.

Change from baseline to Week 14 end of infusion treatment:

The secondary endpoint analysis is the overall treatment comparison between HB-adMSCs treatments and placebo after Week 14 of infusion. A pair-wise comparison of HB-adMSCs 200MM vs Placebo, HB-adMSCs 100MM vs Placebo and HB-adMSCs 50MM vs Placebo are also described in this table.

Secondary endpoint will be analysed using the standard ANCOVA model followed by Tukey's multiple comparison test to test the the significance of the effects of the

Protocol Number: HBCOVID02
Hope Biosciences
Statistical Analysis Plan

Confidential

Date: 14-Oct-2021
Version: 1.0
Status: Final

treatment. The model includes treatment as fixed factor and the baseline value as a covariate.

Sensitivity/supportive analysis model

Change from baseline values of treatment will be analysed using the standard ANCOVA model based on efficacy analysis set followed by Tukey's multiple comparison test to test the the significance of the effects of the treatment. The model includes treatment as fixed factor and the baseline value as a covariate. A pair-wise comparison of HB-adMSCs 200MM vs Placebo, HB-adMSCs 100MM vs Placebo and HB-adMSCs 50MM vs Placebo are also described in this table for secundar endpoints.

A repeated measurements analysis (RMA) of value and change from baseline over Week 26 of treatment will be performed on the efficacy analysis sets, followed by Tukey's multiple comparison test to test the the significance of the effects of the treatment.

All observed measurements available post baseline and change from baseline, at scheduled measurement times, will also be analysed in a linear mixed model using an unstructured residual covariance matrix. The model will include treatment, visit as fixed factors and baseline as a covariate. Furthermore, the model will include interaction terms between treatment and visit, and between baseline and visit. Subject will be included as a random factor when fitting the model.

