Allogeneic HB-adMSCs to provide immune support against COVID-19.

- The patient develops a severe allergic reaction that occurs following investigational product administration.

A patient may voluntarily withdraw or be withdrawn from the study at any time for reasons including, but not limited to, the following:

- Patient withdrawal of consent: At any time, a patient's participation in the study may terminate at his/her request. The specific reason for patient withdrawal will be noted on the case report form (CRF).
- Lost to follow-up: The patient stops coming for visits, and study personnel is unable to contact the patient after repeated attempts (e.g., mail, or email).
- This study may be terminated at the discretion of the Sponsor or any regulatory agency.

If a patient's infusions are discontinued at any point during the trial and the patient maintains consent to contribute additional outcome information, the patient should continue to be followed through Week 26 for all safety and efficacy assessments. Investigators will be trained about the importance of retention and steps to prevent missing data.

The date and reason for withdrawal are to be documented in the CRF. The study site must immediately notify the medical monitor. The patients who withdraw prematurely must attend an early discontinuation visit if possible, at which time they will complete all assessments described in Table 2 under the Week 24 visit.

In the event that a patient discontinues prematurely from the study due to an Adverse Event (AE) or serious AE, the event will be followed until it resolves (returns to normal or baseline values) or stabilizes, or until it is judged by the Investigator to be no longer clinically significant. Once a patient is withdrawn from the study, the patient may not re-enter the study. If the subject develops symptoms associated with COVID-19 during the conduct of this study, they will be asked to consult their personal physician and be tested for COVID-19, and to self-quarantine for at least 14 days. Quarantine must occur while waiting for COVID-19 test results. Once asymptomatic, subject may resume site visits. If the test results are positive, the subject will be asked to quarantine and may continue to receive infusions at the quarantine site. If the subject develops severe symptoms (i.e., shortness of breath/difficulty breathing) they should go to the ER instead of personal physician.

Treatments

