4. ANALYSIS POPULATIONS

Population	Definition / Criteria	Analyses Evaluated
Safety analysis set	
• All randomised subjects who received at least one dose of HB-adMSCs infusion or placebo.• If participants receive a treatment different to their randomized treatment, they will be analysed according to the treatment actually received.	
• Safety• Study Population
Efficacy analysis set	
• All randomized participants who received all 5 infusions of HB-adMSCs or placebo.• Participants will be analysed according to their randomized treatment.	
• Efficacy

Protocol Number: HBCOVID02
 Hope Biosciences
 Statistical Analysis Plan

Confidential

Date: 14-Oct-2021
 Version: 1.0
 Status: Final

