5.5 General Considerations

Unless otherwise stated, all hypotheses will be tested at a 2-sided significance level of 0.05 and 95% confidence interval. All continuous measurements will be summarised descriptively at each visit by treatment using observed data.

Summary of continuous variables will be presented using N, Mean, Standard Error of mean (SE), Standard Deviation (SD), Median and Range (Minimum and Maximum). The categorical variables will be presented using number and percentage based on N.

For measurements over time mean values will be plotted to explore the trajectory over time. LOCF imputed data will be used as the basis for plotting data along with bars as standard error (SE) or Standard Deviation (SD), if not otherwise specified.

Primary endpoints of incidence of COVID-19 symptoms and Hospitalizations due to COVID-19 symptoms will be analysed based on binomial model and p-value will be displayed using two-sample binomial proportion test.

Additionally, time to first incidence of COVID-19 symptoms will analysed using Kaplan-Meir method.

A standard analysis of covariance (ANCOVA) model will be applied for secondary endpoints followed by Tukey's multiple comparison test to test the the significance of the effects of the treatment. The model includes treatment as fixed factor and the corresponding baseline value as a covariate.

Tukey's multiple comparison tests will be tested as two-sided hypotheses at a 5% level of significance. Treatment differences will be confirmed and considered significant if p-value reported is < 0.05 .

Protocol Number: HBCOVID02
Hope Biosciences
Statistical Analysis Plan

Confidential

Date: 14-Oct-2021
Version: 1.0
Status: Final

Presentation of results from a statistical analysis will include the estimated mean treatment effects (Least Square Means (LSMeans)) for absolute values and change from baseline. For all endpoints analysed statistically, estimated mean treatment differences will be presented together with two-sided 95% confidence intervals and p-values obtained using Tukey's method, and results from following paired comparisons will be displayed,

1. HB-adMSCs 200MM vs Placebo
2. HB-adMSCs 100MM vs Placebo
3. HB-adMSCs 50MM vs Placebo

All safety evaluations will be presented using Safety Analysis Set. The efficacy analysis will be presented using Efficacy analysis set.

Individual safety and efficacy parameters will be listed.

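### The first sensitivity ANCOVA for the secondary endpoints repeats the main ANCOVA, and no analysis in SAP Section 7.2 tests the exclusion of participants with fewer than five infusions

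*SAP*

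**What the plan says.** **Main secondary analysis.** For change from baseline to Week 26, and again to Week 14, SAP 7.2.4.1 states: "Secondary endpoint will be analysed using the standard ANCOVA model followed by Tukey's multiple comparison test". On the terms: "The model includes treatment as fixed factor and the baseline value as a covariate". Each dose is compared with placebo. SAP 7.2.3 sets the population: "The secondary efficacy analyses will be based on the Efficacy analysis set population, unless otherwise specified". SAP Section 4 defines that set as: "All randomized participants who received all 5 infusions of HB-adMSCs or placebo".

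**First sensitivity/supportive analysis (SAP 7.2.4.1).** "Change from baseline values of treatment will be analysed using the standard ANCOVA model based on efficacy analysis set". Tukey's test, the sentence on model terms and the three dose-versus-placebo contrasts then follow as before. No visit is named.

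**Other supportive analyses.** The same subsection adds a repeated-measures analysis, explicitly on the efficacy set. It also adds a linear mixed model with unstructured covariance and with treatment-by-visit and baseline-by-visit terms. No set is named for the mixed model.

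**Follow-up after infusions stop.** In the protocol section on withdrawal, removal and replacement, when infusions are discontinued and consent for outcome data is maintained, "the patient should continue to be followed through Week 26 for all safety and efficacy assessments".

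**The concern.** A sensitivity analysis should change an assumption and show whether the result survives. This one changes nothing that the text specifies. If the report listed it as supporting the main result, a reader could take automatic agreement for robustness.

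The assumption most in need of testing is the restriction to people who received all five infusions. That condition is settled only at Week 14, after randomisation. The protocol gives reasons for missing an infusion that may relate to treatment or outcome: an ongoing adverse event can lead to an infusion being held, a severe allergic reaction ends treatment, and a participant with symptoms on the morning of a visit is asked to stay at home. Infusions may continue at a quarantine site after a positive test, so not every symptomatic participant is lost, but some can be. The secondary endpoints include CRP, IL-6 and TNF-alpha, and the protocol's efficacy assessments section describes CRP as an early sign of infection or inflammation. Removing such participants could therefore bias these comparisons, and nothing planned in Section 7.2 would show it.

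**Working it through.** The plan states no figure to reproduce here. The check compares the two specifications and then asks what each supportive analysis can detect.

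**1. The two ANCOVAs side by side**

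| Item | Main (SAP 7.2.3, 7.2.4.1) | First sensitivity analysis (SAP 7.2.4.1) |
|---|---|---|
| Outcome | Change from baseline, Week 26 and Week 14 | Change from baseline, visit not named |
| Terms | Treatment, baseline | Treatment, baseline |
| Post-test | Tukey | Tukey |
| Dose contrasts | Each dose vs placebo | Each dose vs placebo |
| Set | Efficacy set, by default | Efficacy set, by name |
| Level (SAP 5.5) | Two-sided 0.05 | Two-sided 0.05 |
| Missing-data rule | None stated | None stated |

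The level comes from the general rule that "all hypotheses will be tested at a 2-sided significance level of 0.05". The only imputation statement is "LOCF imputed data will be used as the basis for plotting data", which concerns figures and does not separate the two models.

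**2. Would absolute values make a difference?** No. Let Y be the follow-up value, B the baseline and D = Y − B. If D = α + τ + βB + e, then Y = α + τ + (β + 1)B + e. The treatment effect τ and the residuals are unchanged, so the standard error and p-value are too.

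**3. Numerical check.** 500 trials were simulated with 53 participants in arms of 13, 13, 13 and 14. The assumptions are mine: between-subject SD 1, residual SD 0.7, no treatment effect, and a chance of incomplete infusions that rises with the underlying state (logit = −2 + state). The efficacy set averaged 44.6 participants.

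- Same ANCOVA on the same set: maximum difference in estimate and p-value = 0.
- Change versus absolute value, both adjusted for baseline: maximum difference 4 × 10⁻¹⁵, which is rounding error.
- Mixed-model structure with complete visits, against the Week 26 ANCOVA (50 trials): maximum difference in estimate 1 × 10⁻¹⁵.
- The same comparison with about 10% of Week 26 values missing: mean absolute difference about 0.07.
- Week 26 ANCOVA on all 53 instead of the efficacy set: mean absolute shift in one dose-versus-placebo estimate about 0.13.

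The identities do not depend on these assumptions. The 0.07 and 0.13 do. The 0.13 is an absolute shift under exclusion that works alike in every arm; it shows that changing the set can move the estimate and is not an estimate of bias in this trial.

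**4. How many participants?** The documents give no rate of incomplete infusions. Taking the protocol's 15% drop-out as a stand-in gives 53 × 0.15 = 7.95, about 8 outside the set, leaving 53 × 0.85 = 45.05. Half that rate gives 53 × 0.075 = 3.98, about 4; double gives 53 × 0.30 = 15.9, about 16. All three are illustrations.

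**The case against.** - **Identity is conditional.** The sensitivity paragraph names no visit and neither ANCOVA has a missing-data rule. A reader might infer that the difference is zero whatever is done; that goes beyond the text. The objection stands as a condition. At another visit, though, the result would concern a different endpoint and would not check the main one.
- **The section is not empty.** A reader might infer that all of the supportive analyses are redundant. They are not: the repeated-measures analysis and mixed model are different models, and the mixed model can add information where visits are missing. Its use of the efficacy set is an inference from the 7.2.3 default, though the likelier reading. On that reading it still cannot test an exclusion applied before the data reach it.
- **Drop-out is a different event.** A participant who leaves after Week 14 may have had all five infusions and stay in the set; one who misses a single infusion leaves the set without dropping out. This stands. A reader might infer that about 8 participants will be excluded, and the documents do not support that.
- **Section 6.1.** A reader might also infer that people with fewer than five infusions appear in no efficacy analysis anywhere. SAP 6.1, whose analyses use the Safety set, describes binomial tests for the primary endpoints and a treatment-only ANCOVA for secondary endpoints. This conflicts with SAP 5.5 and 7.2 and may be a drafting slip, but it limits the claim to Section 7.2.
- **Low stakes.** These are secondary endpoints, tested as exploratory under SAP 5.4, and the plan nowhere commits to claiming confirmation. That tempers the priority but does not justify a duplicate analysis. The five-infusion set also governs the primary analysis (SAP 7.1.3), which this point does not address.

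**Conclusion.** The point holds within those limits. At Week 26 or Week 14, with the same missing-data handling, the first sensitivity ANCOVA differs from the main one by 0 and tests nothing. No analysis in Section 7.2 tests the effect of excluding participants with fewer than five infusions; for the mixed model this rests on the 7.2.3 default. The number excluded and the size of any bias cannot be derived from the documents. The plan should be changed, but given the exploratory status of these endpoints this is not a fatal defect.

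**What to change.** 1. Add to SAP Section 4 a set of everyone randomised who had at least one infusion, active or placebo, analysed in the arm assigned. The Safety set has this entry rule but is analysed by treatment received, so renaming the set in 7.2.4.1 is not enough.
2. Replace the duplicate ANCOVA with the same model on the new set at Week 26 and Week 14, naming the visits and the handling of missing values.
3. Run the mixed model on the new set as well, using all observed values to Week 26, including those after infusions stopped. State its set explicitly.
4. Report how many participants in each arm the efficacy set excludes, and why.
5. Reconcile the treatment-only, Safety-set ANCOVA in SAP 6.1 with Section 7.2.

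The cost is one set definition, a short SAP amendment and a rerun of existing programs; no new data collection is needed. The gain is limited by consent: participants who withdraw it may contribute no Week 26 value, so the number added is unknown in advance.

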8. SAFETY ANALYSES

The safety analyses will be based on the Safety analysis set, unless otherwise specified.

8.1. Adverse Events Analyses

Adverse events (AES) are summarised descriptively. AE data will be displayed in terms of the number of subjects with at least one event (N), percentage of subjects with at least one event (%), the number of events (E) and the event rate per 100 years of exposure (R).

Summaries of AEs and of serious AEs will be presented as an overview including all AEs, serious AEs, AEs by severity, AEs by relation to treatment, action to AEs and treatment advised, and outcome of AEs.

Furthermore, summary tables based on reported terms are made for:

- All AEs
- Serious AEs
- AEs leading to withdrawal of study

Individual adverse events will be listed.

The details of the planned displays are in Appendix 5: List of Data Displays.

Protocol Number: HBCOVID02
Hope Biosciences
Statistical Analysis Plan

Confidential

Date: 14-Oct-2021
Version: 1.0
Status: Final

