Unblinding of patient and researcher will occur in the case of adverse event suspected to be related to the investigational product, per the medical monitor and DSMB.

Regulatory authorities and/or the IRB may request the unblinding of data from one or more patients at any time.

Prior and concomitant conditions

The investigators should document all prior significant medical history. Additional conditions present at the time when informed consent is given and up to the time of first infusion (Week 0) are to be regarded as concomitant conditions. Illnesses first occurring or detected during the study and/or worsening of a concomitant condition during the study should be documented as AEs in the CRF.

Prior and concomitant medications

All medications, including over-the-counter treatments and preventative vaccines taken by the patient during the study, including those treatments initiated prior to the start of the study, must be recorded in the CRF. The entry must include the dose, regimen, route, indication, and dates of use.

Study Procedures

Table 2 outlines the timing of procedures, and assessments to be performed throughout the study.

Table 2. Schedule of Assessments

Visit Number	1	2	3	4	5	6	7	8	9
Weeks	N/A	Week 0	Week 2	Week 6	Week 10	Week 14	Week 18	Week 22	Week 26
Visit Name	Screening (Phone call)	Infusion-1 /Baseline	Infusion 2	Infusion 3	Infusion 4	Infusion 5	Follow Up	Follow Up	EOS
Window Period	Up to 45 days	±4 days	±4 days	±4 days	±4 days	±4 days	±4 days	±3 days	±3 days
STUDY PROCEDURES									
Informed Consent	X	X							
Inclusion and Exclusion Criteria	X	X							
Pre-infusion assessment		X	X	X	X	X			
Review of Medical History	X	X	X	X	X	X	X	X	X
Concomitant Medication Review	X	X	X	X	X	X	X	X	X

Allogeneic HB-adMSCs to provide immune support against COVID-19.

Vital Signs		X	X	X	X	X	X	X	X
Weight and Height ¹		X	X	X	X	X	X	X	X
Physical Examination		X	X	X	X	X	X	X	X
SF-36 Questionnaire		X	X	X	X	X	X	X	X
PHQ-9		X	X	X	X	X	X	X	X
Rapid antibody COVID-19		X							X
CBC with differential		X		X		X			X
Chemistry		X		X		X			X
Coagulation Panel		X		X		X			X
CRP		X		X		X			X
IL-6		X		X		X			X
IL-10		X		X		X			X
TNF alpha		X		X		X			X
HB-adMSCs Administration		X	X	X	X	X			
24-hour telephone encounter		X	X	X	X	X			
Adverse Event Monitoring		X	X	X	X	X	X	X	X
1. Height will only be measured at baseline									

Informed Consent (ICF)

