A complete physical examination (head, eyes, ears, nose, throat, heart, lungs, abdomen, skin, cervical and axillary lymph nodes, neurological, and musculoskeletal systems) will be performed

Allogeneic HB-adMSCs to provide immune support against COVID-19.

at baseline visit. In addition, medical history (including smoking history) will be recorded at baseline.

A limited physical examination to verify continued patient eligibility and to follow up any change in medical history will be performed at the visits indicated in the schedule of assessments. Symptom-driven physical examinations will be performed as clinically indicated at any study visit. All changes not present at baseline or described in the past medical history and identified as clinically noteworthy will be recorded as AEs.

Clinical Laboratory Parameters

The Investigator must review all laboratory reports and document the review. Any laboratory test result or change considered by the Investigator to be clinically significant should be considered an AE and recorded in the AE CRF. Clinically significant abnormal values occurring during the study will be followed until repeat test results return to normal, stabilize, or are no longer clinically significant.

Laboratory tests to be performed during the study:

Complete Blood Count with Differential	IL-6
Chemistry	IL-10
Coagulation study (PTT/PT/INR)	Tumor Necrosis Factor alpha
C Reactive Protein	Rapid Antibody Test for COVID-19

Adverse Events

An AE is any symptom, physical sign or disease that either emerges during the study or, if present at screening, worsens during the study, regardless of the suspected cause of the event. All medical and psychiatric conditions (except those related to the indication under study) present at screening will be documented in the medical history CRF. Changes in these conditions and new symptoms, physical signs, or diseases should be noted on the AE CRF during the rest of the study.

Clinically significant laboratory abnormalities should also be recorded as AEs. Surgical procedures that were planned before the patient enrolled in the study are not considered AEs if the conditions were known before study inclusion; the medical condition should be reported in the patient's medical history.

Serious Adverse Events (SAE)

A serious adverse event (SAE) is any AE that is:

Allogeneic HB-adMSCs to provide immune support against COVID-19.

- fatal
- life-threatening
- requires or prolongs hospital stay

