The risks associated with this cellular product are currently unknown and have not been studied in this population, to date. There is a potential risk of increased vulnerability to COVID-19, worsening of the disease, and/or complications from the disease. Although currently not

Allogeneic HB-adMSCs to provide immune support against COVID-19.

observed in HB-adMSCs, risks of infusion with MSCs include infusion-related reactions, thrombogenesis or malignancy.

The types of risk associated with HB-adMSCs are also stated in the Informed Consent Form (See ICF)

Minimization of Risks

Although the risk to subjects participating in the study is anticipated to be minimal, the clinician, at his/her discretion, will not collect data from those individuals for whom collection is judged to pose an unusually high risk of physical or mental harm or discomfort.

Participation in this study poses moderate risk to study personnel related to potential pathogens that may be present in the subject's specimens which are then expanded during the culture process. These risks will be minimized by adherence to the principles of universal precautions and by conducting the planned testing on blood from the subject at screening for particular pathogens of concern.

Personnel should wear appropriate personal protective equipment to avoid contact of the eyes or skin with hazardous materials or products derived from biological sources.

Subjects will be advised to follow current federal guidelines regarding COVID-19 such as the following:

- Use hand sanitizer that contains at least 60% alcohol
- Avoid touching your eyes, nose, and mouth with unwashed hands
- Avoid close contact
- Adhere to social distancing guidelines and maintain at least 6' of distance with others

General procedures for personnel include:

- Hands must be washed with soap and water for at least 20 seconds, if soap and running water are unavailable, an alcohol-based hand rub with at least 60% alcohol will suffice this action. Always wash hands that are visibly soiled.
- Avoid touching their eyes, nose or mouth.
- Healthcare workers will wear:
 - o Gowns
 - o Gloves
 - o Disposable surgical masks.
 - o Eye/face protection (e.g., goggles, face shield)
- Surfaces where subjects have been in contact will be disinfected 70% Isopropyl Alcohol, hydrogen peroxide, or Clorox disinfectant.

Allogeneic HB-adMSCs to provide immune support against COVID-19.

Potential Benefits

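### SAP 8.1 plans no AE or SAE total without COVID-19, so any effect of the product on the primary efficacy events shifts those totals

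*SAP*

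**What the plan says.** SAP 8.1 summarises AEs descriptively as subjects with an event, percentage, number of events and rate per 100 years of exposure. It states: "Summaries of AEs and of serious AEs will be presented as an overview including all AEs, serious AEs, AEs by severity", and continues with relation to treatment, action taken and outcome. It adds tables by reported term for all AEs, serious AEs and AEs leading to withdrawal, plus individual listings. SAP 5.1 sets the four arms as display columns. SAP 8.1 does not mention COVID-19.

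What counts as an AE comes from the protocol:

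- Adverse Events: "An AE is any symptom, physical sign or disease that either emerges during the study", whatever the suspected cause.
- Prior and concomitant conditions section: "Illnesses first occurring or detected during the study and/or worsening of a concomitant condition during the study should be documented as AEs in the CRF".
- Serious Adverse Events: an AE is serious if, among other criteria, it "requires or prolongs hospital stay". AEs are collected from consent through Week 26.
- The only exception for the studied indication concerns history taken at entry: "All medical and psychiatric conditions (except those related to the indication under study) present at screening will be documented in the medical history CRF".

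On efficacy, SAP 7.1.1 says: "The primary endpoints are incidence of COVID-19 symptoms and Hospitalizations due to COVID-19 symptoms". The protocol's Risks section also treats COVID-19 as a possible harm of the product: "There is a potential risk of increased vulnerability to COVID-19". That sentence goes on to worsening and complications of the disease.

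**The concern.** The same illness is counted as an efficacy outcome in SAP 7.1 and as an AE in SAP 8.1. The all-AE and SAE percentages by arm therefore mix two things: events the product may prevent or promote through COVID-19, and all other events. The synopsis expects the trial to show whether the product is safe in people at increased risk of infection. A statement that AE incidence was similar to placebo could describe a product with no excess of other events. It could equally describe one whose excess was partly offset by fewer COVID-19 cases. The totals alone cannot tell these apart.

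Subtracting the efficacy counts does not recover the difference. The safety set is everyone dosed, while the efficacy set is restricted to those who received all five infusions (SAP 4). A subject may also have both kinds of event.

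**Working it through.** **Step 1: do COVID-19 events enter the totals?** An on-study illness is an AE, an admission is an SAE, and the collection period covers the efficacy period. The one exception applies to conditions present at screening. SAP 8.1 adds no exclusion. So they do enter, by inference from the protocol.

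**Step 2: how far do the totals move?** The documents give no AE or COVID-19 rates, so every rate here is an assumption. Let b be the risk of at least one non-COVID AE and c the risk of COVID-19, taken as independent. Then

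P(any AE) = 1 - (1 - b)(1 - c).

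Take b = 30% on placebo and 40% on product, a true excess of 10 points. RR is the COVID-19 risk ratio, product to placebo.

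| Placebo c | RR | Placebo total | Product total | Difference |
|---|---|---|---|---|
| 10% | 1 | 1 - 0.70×0.90 = 37.0% | 1 - 0.60×0.90 = 46.0% | +9.0 |
| 10% | 0.5 | 37.0% | 1 - 0.60×0.95 = 43.0% | +6.0 |
| 20% | 0.5 | 1 - 0.70×0.80 = 44.0% | 1 - 0.60×0.90 = 46.0% | +2.0 |
| 30% | 0.5 | 1 - 0.70×0.70 = 51.0% | 1 - 0.60×0.85 = 49.0% | -2.0 |
| 30% | 0.3 | 51.0% | 1 - 0.60×0.91 = 45.4% | -5.6 |
| 10% | 2 | 37.0% | 1 - 0.60×0.80 = 52.0% | +15.0 |

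For SAEs, assume non-COVID risks of 2% on placebo and 5% on product (+3 points), with RR 0.5 for COVID-19 admission:

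- Placebo admission risk 2%: 1 - 0.98×0.98 = 3.96% against 1 - 0.95×0.99 = 5.95%, about +2.0 points.
- 5%: 1 - 0.98×0.95 = 6.90% against 1 - 0.95×0.975 = 7.375%, about +0.5.
- 10%: 1 - 0.98×0.90 = 11.8% against 1 - 0.95×0.95 = 9.75%, about -2.

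**Step 3: when does the sign change?** Setting the two totals equal gives a break-even product-arm COVID-19 risk of

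1 - (1 - b_placebo)(1 - c_placebo)/(1 - b_product).

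- For 40% against 30%, the break-even RR is 0.33, 0.61 and 0.75 at placebo COVID-19 risks of 20%, 30% and 40%. At 10% or less, no degree of protection reverses the sign.
- For 45% against 30%, it is 0.36 at 30% and 0.59 at 40%. Reversal is impossible at 20% or less.
- For SAEs at 5% against 2%, it is 0.40 at a 5% admission risk and 0.72 at 10%. Reversal is impossible at 2%.

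**Step 4: sampling noise.** With 53 subjects at 3:1, about 40 receive product and 13 placebo. For a true 45% against 30% excess, exact binomials give a 16% chance that the observed product percentage is at or below placebo when only non-COVID AEs are counted. With COVID-19 included, the chance is 25% (placebo risk 10%, RR 0.5), 44% (30%, RR 0.5) and 53% (30%, RR 0.3).

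**The case against.** The strongest reply is that the plan already separates the two.

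- The AE endpoint in the protocol's Study Endpoints and SAP 2.1 is limited to drug-related events, and so are the protocol's safety hypotheses. The pooled total is not the declared safety measure.
- Tables by reported term would normally put COVID-19 on its own line, so a specific toxicity stays visible in its own row. Every AE is also listed.
- AE summaries are descriptive, with no test. For 40% against 30% with 40 and 13 subjects, the standard error is √(0.40×0.60/40 + 0.30×0.70/13) ≈ 15 points, as large as most of the shifts shown above.
- SAP 8.1 leaves display details to Appendix 5, which is not in the text available for review.

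Most of this stands and limits the weight of the point, but the separation is only partial. Under Causal Relationship of Adverse Events, both the definite and the possible category require a known or expected response pattern. The Risks section says the product's risks are not yet known. An unanticipated toxicity fits neither category well, so the comparison with placebo is needed to detect it. COVID-19 itself could be rated possibly related, given the vulnerability risk named there.

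SAP 8.1 states no coding or COVID-19 grouping for reported terms. Fever, cough and breathlessness are the COVID-19 symptoms named in Study Objectives. High fever is also an infusion stopping sign, and dyspnoea is an anaphylaxis criterion in Appendix 1. One row can hold both kinds of event.

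**Conclusion.** The point holds as a minor one. COVID-19 illness and admission fall within the all-AE and SAE totals, and no total without them is planned in SAP 8.1. A protective effect dilutes an excess of other events, and a harmful effect enlarges the total. The sizes above rest on assumed rates and independence.

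Four stronger readings are not supported:

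- A reader might infer that SAP 8.1 itself says COVID-19 is counted. It does not; the inclusion follows from the protocol's definitions.
- A reader might take the pooled total as the trial's headline safety comparison. The stated endpoint and hypotheses concern drug-related events.
- A reader might expect the comparison of harm to vanish or reverse. That needs high COVID-19 incidence and strong protection; at low incidence the excess only shrinks. The DSMB review triggers of 15 diagnoses and 5 hospitalizations (28% and 9% of 53) set when a review happens and do not forecast incidence.
- A reader might conclude that COVID-19 should be left out of the safety comparison. The protocol names vulnerability to it, its worsening and its complications as possible product harms, so it belongs in the safety data.

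**What to change.** In SAP 8.1:

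1. Show the AE overview, the all-AE total and the SAE total by arm in two versions side by side: all events, and all events except those of test-positive COVID-19. The protocol's withdrawal section already asks symptomatic subjects to be tested.
2. Show test-positive COVID-19 as its own row, with the same four measures.
3. Set the flag for each AE before unblinding, by a written attribution rule.
4. Keep in both versions thromboembolic events and the other product risks named in the protocol's Risks and Endpoints sections (infusion-related reactions, hepatotoxicity, heart failure, cytopenia, and serious infections other than COVID-19 itself), even in a test-positive subject. Keep untested or test-negative fever, cough and breathlessness in both as well, so that infusion reactions are not removed.
5. Read the two versions together. The toxicity conclusion should not rest on the exclusion version alone.

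The cost is SAP wording, one flag per AE and a second run of existing tables. The drawback is that COVID-19 cases never tested stay in the exclusion version.
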